7.1 Efficacy Assessments

7.1.1 Radiographic Disease Assessment

All patients enrolled in the study are to undergo disease evaluations as outlined in the Study Calendars (Section 6.1). If symptoms develop or clinical deterioration occurs, patients may be imaged prior to the pre-specified time points for imaging. Patients discontinuing treatment prior to objective disease progression will be followed by radiographic evaluation until disease progression is documented or until the start of subsequent anti-cancer therapy, whichever is sooner.

Screening/baseline tumor assessments should include CT (with contrast, unless contraindicated) of the chest and abdomen (plus pelvis if indicated) and MRI of the brain

with and without gadolinium (preferred) or head CT with contrast if MRI is contraindicated. The allowable windows for screening/baseline assessments is 28 days prior to randomization.

Disease assessments performed on-study will include CT of the chest/abdomen (plus pelvis if indicated) and assessment of all known and suspected sites of disease. MRI brain should be performed on schedule with other radiologic disease evaluations if there is known CNS disease. If no known CNS metastases, MRI brain should be performed as clinically indicated. Assessments will be performed as per study calendars: every 6 weeks (starting from C1D1) for 3 months, every 9 weeks for 9 months and every 12 weeks thereafter. The allowable windows for on-study assessments is +/- 7 days. Assessments will be performed until objective disease progression is documented by the Investigator, or subsequent anti-cancer therapy is begun.

The Investigator's assessment of disease response and progression per RECIST 1.1 (for extracranial disease) and RANO-BM criteria (for intracranial disease) will be the basis for patient management and statistical analyses of radiology-based study endpoints. RECIST v1.1 and RANO-BM criteria are summarized in Appendices 3 and 4.

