9.2.8 Intracranial Progression Free Survival

Intracranial Progression Free Survival (iPFS) in all patients regardless of the presence of baseline CNS metastases is an exploratory endpoint of this study. iPFS is defined as the time from first dose to the date of first intracranial progressive disease (as per RANO-brain metastasis criteria). An approach similar to that described for the analysis of PFS (Section 9.2.3) will be used.

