- Stable Disease (SD): Does not qualify for CR, PR or Progression. All target lesions must be assessed. Stable can follow PR only in the rare case that the sum increases by less than 20% from the nadir, but enough that a previously documented 30% decrease no longer holds.
- Progressive Disease (PD): 20% increase in the sum of diameters of target measurable lesions above the smallest sum observed (over baseline if no decrease in the sum is observed during therapy) with a minimum absolute increase of 5 mm.
- Not evaluable:
 - one or more target lesions have not been assessed,
 - or assessment methods used were inconsistent with those used at baseline and impaired assessment,
 - or one or more target lesions cannot be measured accurately (e.g., poorly visible unless due to being too small to measure),
 - or one or more target lesions were excised or irradiated and have not reappeared or increased.

Non-Target Disease

- CR: Disappearance of all non-target lesions and normalization of tumor marker levels. All lymph nodes must be 'normal' in size (<10 mm short axis).
- Non-CR/Non-PD: Persistence of any non-target lesions and/or tumor marker level above the normal limits.

- PD: Unequivocal progression of preexisting lesions. Generally, the overall tumor burden must increase sufficiently to merit discontinuation of therapy. In the presence SD or PR in target disease, progression due to unequivocal increase in non-target disease should be rare.
- Not evaluable: One or more non-target sites were not assessed or assessment methods were inconsistent with those used at baseline.

New Lesions

The appearance of any new unequivocal malignant lesion indicates PD. If a new lesion is equivocal, for example due to its small size, continued assessment will clarify the etiology. If repeat assessments confirm the lesion, then progression should be recorded on the date of the initial assessment. A lesion identified in an area not previously scanned will be considered a new lesion.

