
Non-target lesions should be assessed qualitatively at each of the timepoints specified in the protocol.

- Complete response: Requires all of the following: disappearance of all enhancing CNS non-target lesions, no new CNS lesions.
- Non-complete response or non-progressive disease: Persistence of one or more non-target CNS lesion or lesions.
- Progressive disease: Any of the following: unequivocal progression of existing enhancing non-target CNS lesions, new lesion(s) (except while on immunotherapy-based treatment), or unequivocal progression of existing tumor-related non-enhancing (T2/FLAIR) CNS lesions. In the case of immunotherapy-based treatment, new lesions alone may not constitute progressive disease.

12.5 Appendix 5: Medications or Substances to be Avoided or Used with Caution During Treatment with Sitravatinib

Drugs with a Known Risk of Torsades de Pointes*

Generic Name	Brand Names (Partial List)	Drug Class	Therapeutic Use
Aclarubicin (Only on Non US Market)	Aclacin, Aclacinomycine, Aclacinon, Aclaplastin, Jaclacin	Anti-cancer	Cancer
Amiodarone	Cordarone, Pacerone, Nexterone	Antiarrhythmic	Arrhythmia
Anagrelide	Agrylin, Xagrid	Phosphodiesterase 3 inhibitor	Thrombocythemia
Arsenic trioxide	Trisenox	Anti-cancer	Cancer (leukemia)
Astemizole (Removed from US Market)	Hismanal	Antihistamine	Allergic rhinitis
Azithromycin	Zithromax, Zmax	Antibiotic	Bacterial infection
Bepridil	Vascor	Antiangular	Angina Pectoris (heart pain)
Cesium Chloride	Energy Catalyst	Toxin	Alternative therapy cancer
Chloroquine	Aralen	Antimalarial	Malaria
Chlorpromazine	Thorazine, Largactil, Megaphen	Antipsychotic / Antiemetic	Nausea, Schizophrenia, many others
Chlorprothixene (Only on Non US Market)	Truxal	Antipsychotic	Schizophrenia
Cilostazol	Pletal	Phosphodiesterase 3 inhibitor	Intermittent claudication
Ciprofloxacin	Cipro, Cipro-XR, Neofloxin	Antibiotic	Bacterial infection
Cisapride (Removed from US Market)	Propulsid	GI stimulant	Increase GI motility
Citalopram	Celexa, Cipramil	Antidepressant, SSRI	Depression
Clarithromycin	Biaxin, Prevpac	Antibiotic	Bacterial infection
Cocaine	Cocaine	Local anesthetic	Anesthesia (topical)
Disopyramide	Norpace	Antiarrhythmic	Arrhythmia
Dofetilide	Tikosyn	Antiarrhythmic	Arrhythmia
Domperidone (Only on Non US Market)	Motilium, Motillium, Motinorm Costi, Nomit	Antiemetic	Nausea, vomiting

Generic Name	Brand Names (Partial List)	Drug Class	Therapeutic Use
Donepezil	Aricept	Cholinesterase inhibitor	Dementia (Alzheimer's Disease)

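### Exploratory iPFS does not count a first on-treatment brain metastasis when it appears in a patient with no baseline brain lesion, because Appendix 4 excepts new lesions during immunotherapy and gives no dating rule

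*Combined protocol and SAP*

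**What the plan says.** Section 9.2.8 sets the population as "Intracranial Progression Free Survival (iPFS) in all patients regardless of the presence of baseline CNS metastases" and classes the endpoint as exploratory. On the event it says "iPFS is defined as the time from first dose to the date of first intracranial progressive disease (as per RANO-brain metastasis criteria"), and it refers to the PFS approach in 9.2.3 for the analysis.

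Section 7.1.1 assigns RECIST 1.1 to extracranial disease and says that "RANO-BM criteria (for intracranial disease) will be the basis for patient management and statistical analyses of radiology-based study endpoints". Both sets of criteria are summarised in appendices.

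Appendix 4 includes among the grounds for intracranial progression "new lesion(s) (except while on immunotherapy-based treatment"). It then says: "In the case of immunotherapy-based treatment, new lesions alone may not constitute progressive disease".

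For comparison, Appendix 3 (RECIST 1.1) says "The appearance of any new unequivocal malignant lesion indicates PD", and dates a lesion that was equivocal at first to the initial assessment once repeat assessments confirm it. Appendix 4 has no counterpart to that dating rule.

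Under 5.2.2, all patients start pembrolizumab on Day 1 and continue for up to 35 three-week cycles.

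**The concern.** For a patient who enters without brain metastases, iPFS means freedom from a first brain metastasis. A new lesion is the only way such a patient can begin to progress in the brain. The Appendix 4 exception removes that event for as long as the patient is on immunotherapy, which every patient receives from the first dose.

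The exception makes sense where existing lesions are being followed and inflammatory change could be mistaken for progression. Applied unchanged to a time-to-event endpoint in patients with nothing to follow, it delays or removes events. Section 3.3 hypothesises improved iPFS, so the error works in favour of the stated hypothesis.

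**Working it through.** The plan gives no sample size, power or event count for iPFS, so there is no figure to reproduce. The check is to list each route to intracranial progression in Appendix 4 and ask whether it is open to a patient with no baseline brain lesion who is on pembrolizumab.

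| Route in Appendix 4 | Needs | Open at first appearance? |
|---|---|---|
| Growth in the sum of CNS target lesions | Target lesions chosen at baseline | No |
| Clear progression of enhancing non-target lesions | Lesions already present | No |
| Clear progression of non-enhancing (T2/FLAIR) lesions | Lesions already present | No |
| New lesions | Not on immunotherapy | No, excepted |

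So 0 of 4 routes score the first appearance as an event. The period concerned is up to 35 × 3 = 105 weeks of pembrolizumab. A lesion that first appears after immunotherapy has ended would count.

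**What happens next to such a patient**

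1. *Later growth.* The lesion could qualify through a route for existing lesions, but Appendix 4 does not say when a new lesion becomes an existing one. If it does qualify, the event is dated at the later scan. Once the lesion is known, note 14 of both study calendars puts brain imaging on the regular schedule. The nominal delay is then at least one imaging interval: 6, 9 or 12 weeks, depending on time since C1D1 (7.1.1). It could be shorter if the repeat scan at more than 4 weeks in 6.8, or a symptom-driven scan, is done.
2. *Local therapy.* Sections 5.4.2.2 and 6.8 allow selected progressing lesions to be treated locally while the patient stays on trial. A lesion treated before it grows may never meet any route.
3. *New anticancer therapy.* Sections 6.9.1 and 7.1.1 end disease assessment when new therapy starts, so later growth need not be recorded.
4. *No recorded event.* Under the approach borrowed from 9.2.3, the patient is censored at the last tumor assessment.

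**Internal consistency.** Appendix 4 requires the absence of new lesions for intracranial CR and PR, with no immunotherapy exception. The same new lesion therefore rules out a response but is not progression. The two sentences on new lesions also differ in strength: the first is a flat exception, while the second can be read as leaving discretion. Neither tells the analyst how to score or date the lesion.

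**The case against.** The strongest reply has several parts.

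- *The second sentence allows judgement.* New lesions alone may not be progression, which leaves room to count them with other evidence. This is fair as far as it goes: the text is ambiguous as well as restrictive. But on neither reading does any text make a first on-treatment brain metastasis an event, or give its date.
- *Appendix 4 is only an abbreviated summary.* The full criteria may contain a confirmation rule. That cannot be checked here. The gap is shown for the summary that 7.1.1 points to.
- *The endpoint is exploratory.* It has no control, benchmark, test or decision rule, so the impact is limited. This stands.

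Four stronger readings might be inferred, and the documents do not support them.

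- *That the same scan is a PFS event and an iPFS censoring.* Appendix 3 taken alone would make the lesion PD, but 7.1.1 limits RECIST to extracranial disease and 9.2.3 does not say which criteria apply to brain lesions for PFS. The conflict is possible, not established.
- *That imaging stops at the new lesion.* Section 7.1.1 does say "Assessments will be performed until objective disease progression is documented by the Investigator". But if the lesion is not progression, assessments continue, and if it is called progression, 6.8 asks for a repeat scan. Late dating is the likelier fault, with loss where other therapy intervenes.
- *That iPFS stays at 100% in patients without baseline CNS disease.* Section 9.2.8 does not name death as an event, but it borrows the PFS approach, in which death is one. The statement can concern only the intracranial-progression component.
- *That a number of affected patients can be given.* Assuming 10–30% of 70 patients have baseline CNS disease and 5–15% of the rest develop a first brain metastasis on treatment gives 70 × 0.70 × 0.05 = 2.45 to 70 × 0.90 × 0.15 = 9.45 patients. Neither input is in the documents, and a count of patients is not the size of the bias.

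**Conclusion.** The point holds in a limited form. On the stated rule, a first brain metastasis on pembrolizumab in a patient without baseline CNS lesions is not an iPFS event when it appears. It is counted late or missed, so the intracranial-progression component of iPFS is biased upward. The amount depends on how often such metastases occur on treatment and how they are then managed, and the documents give neither.

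The conclusion rests on reading Appendix 4 as the operative rule, as 7.1.1 indicates, and on pembrolizumab counting as immunotherapy-based treatment. Brain imaging only as clinically indicated in patients without known CNS disease is a separate limit on event capture; adding scans would not cure this one. Primary ORR and the two-stage designs are unaffected. The correction is worth making before analysis, but nothing in the trial's main conclusion turns on it.

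**What to change.** In 9.2.8, state for endpoint scoring only that:

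- in patients without baseline CNS lesions, an unequivocal new CNS metastasis is an iPFS event dated at the scan on which it first appears;
- an equivocal new lesion is dated back to its first appearance once a later scan confirms it, as Appendix 3 already does.

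In Appendix 4, reconcile the two sentences on new lesions during immunotherapy. Leave the exception in place for patients with baseline CNS disease: reversing it there is a trade-off that this point does not settle. Because 7.1.1 also uses these criteria for patient management, the new text should say that it governs the iPFS analysis and not treatment decisions.

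The cost is a few lines of protocol and SAP wording, with no added scans. An occasional inflammatory lesion may be counted as progression. A sensitivity analysis that applies the Appendix 4 exception to all patients would show how much that matters.

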12.6 Appendix 6 – Pill Diary

STUDY MEDICATION CALENDAR
(Research Nurse to fill out all this top information)

Patient's Name/ ID#: _____
 HIC# _____
 Cycle# _____
 Total #Pills Dispensed/Cycle _____
 Total #Pills Returned/Cycle _____
 Total # Pills Taken/Cycle _____
 RN signature/Date _____

Day of the week Day of Cycle 1	Day of the week Day of Cycle 2	Day of the week Day of Cycle 3	Day of the week Day of Cycle 4	Day of the week Day of Cycle 5	Day of the week Day of Cycle 6	Day of the week Day of Cycle 7
____ # of Pills Taken ____ :____ AM ____ :____ PM	____ # of Pills Taken ____ :____ AM ____ :____ PM	____ # of Pills Taken ____ :____ AM ____ :____ PM	____ # of Pills Taken ____ :____ AM ____ :____ PM	____ # of Pills Taken ____ :____ AM ____ :____ PM	____ # of Pills Taken ____ :____ AM ____ :____ PM	____ # of Pills Taken ____ :____ AM ____ :____ PM
Day of Cycle 8	Day of Cycle 9	Day of Cycle 10	Day of Cycle 11	Day of Cycle 12	Day of Cycle 13	Day of Cycle 14
____ # of Pills Taken ____ :____ AM ____ :____ PM	____ # of Pills Taken ____ :____ AM ____ :____ PM	____ # of Pills Taken ____ :____ AM ____ :____ PM	____ # of Pills Taken ____ :____ AM ____ :____ PM	____ # of Pills Taken ____ :____ AM ____ :____ PM	____ # of Pills Taken ____ :____ AM ____ :____ PM	____ # of Pills Taken ____ :____ AM ____ :____ PM
Day of Cycle 15	Day of Cycle 16	Day of Cycle 17	Day of Cycle 18	Day of Cycle 19	Day of Cycle 20	Day of Cycle 21
____ # of Pills Taken ____ :____ AM ____ :____ PM	____ # of Pills Taken ____ :____ AM ____ :____ PM	____ # of Pills Taken ____ :____ AM ____ :____ PM	____ # of Pills Taken ____ :____ AM ____ :____ PM	____ # of Pills Taken ____ :____ AM ____ :____ PM	____ # of Pills Taken ____ :____ AM ____ :____ PM	____ # of Pills Taken ____ :____ AM ____ :____ PM
Day of Cycle 22	Day of Cycle 23	Day of Cycle 24	Day of Cycle 25	Day of Cycle 26	Day of Cycle 27	Day of Cycle 28
____ # of Pills Taken ____ :____ AM ____ :____ PM	____ # of Pills Taken ____ :____ AM ____ :____ PM	____ # of Pills Taken ____ :____ AM ____ :____ PM	____ # of Pills Taken ____ :____ AM ____ :____ PM	____ # of Pills Taken ____ :____ AM ____ :____ PM	____ # of Pills Taken ____ :____ AM ____ :____ PM	____ # of Pills Taken ____ :____ AM ____ :____ PM
